### ***Hospitalization, Prolonged Hospitalization or Surgery***

Any adverse event that results in hospitalization or prolonged hospitalization should be documented and reported as a serious adverse event unless specifically instructed otherwise in this protocol. Any condition responsible for surgery should be documented as an adverse event if the condition meets the criteria for an adverse event. As was noted above, events related to the cytotoxic chemotherapy will be excluded from adverse event reporting.

Neither the condition, hospitalization, prolonged hospitalization, nor surgery are reported as an adverse event in the following circumstances:

- Hospitalization or prolonged hospitalization for diagnostic or elective surgical procedures for a preexisting condition. Surgery should **not** be reported as an outcome of an adverse event if the purpose of the surgery was elective or diagnostic and the outcome was uneventful.
- Hospitalization or prolonged hospitalization required to allow efficacy measurement for the study.
- Hospitalization or prolonged hospitalization for therapy of the target disease of the study, unless it is a worsening or increase in frequency of hospital admissions as judged by the clinical investigator.

## **8.2 Recording of Adverse Events**

At each contact with the subject, the investigator must seek information on adverse events by specific questioning and, as appropriate, by examination. Information on all adverse events should be recorded immediately in the source document, and also in the appropriate adverse event module of the case report form (CRF). All clearly related signs, symptoms, and abnormal diagnostic procedures results should be recorded in the source document, though should be grouped under one diagnosis.

All adverse events occurring during the adverse event reporting period (defined in Section 8.1 above) must be recorded. The clinical course of each event should be followed until resolution, stabilization, or until it has been determined that the study treatment or participation is not the cause. Serious adverse events that are still ongoing at the end of the study period must be followed up to determine the final outcome. Any serious adverse event that occurs after the study period and is considered to be possibly related to the study treatment or study participation should be reported immediately.

## **8.3 Reporting of Serious Adverse Events and Unanticipated Problems**

### **8.3.1 Study Sponsor Notification by Investigator**

All serious adverse events must be reported to the study sponsor by email within 24 hours of knowledge of the event. Report serious adverse events by email to:

CONFIDENTIAL

At the time of the initial notification, the following information should be provided:

1. Study identifier
2. Subject number
3. A description of the event
4. Date of onset
5. Current status
6. Whether study treatment was discontinued
7. The reason the event is classified as serious
8. Investigator assessment of the association between the event and study treatment

Within the following 3 business days, the investigator must provide further information on the serious adverse event in the form of a written report. This should include a copy of the completed SAE Form, and any other diagnostic information that will assist the understanding of the event. The investigator will keep a copy of this SAE Form on file at the study site. Significant new information on ongoing serious adverse events should be provided promptly to the study sponsor.

Follow-up information on SAEs should be reported when received, on a copy of the original SAE form, and should include both the follow-up number and report date. The follow-up information should describe whether the event has resolved or continues, if and how it was treated, and whether the patient continued or withdrew from study participation.

### **8.3.2 Investigator reporting: notifying the IRB**

The IRB requires expedited reporting of those events related to study participation that are unforeseen and indicate that participants or others are at increased risk of harm, or where required by the Sponsor. The IRB will not acknowledge safety reports or bulk adverse event submissions that do not meet the criteria outlined below. The IRB requires researchers to submit reports of the following problems within 10 working days from the time the investigator becomes aware of the event:

Any adverse event (regardless of whether the event is serious or non-serious, on-site or off-site) that occurs any time during or after the research study, which in the opinion of the principal investigator is:

Unexpected (An event is “unexpected” when its specificity and severity are not accurately reflected in the protocol-related documents, such as the IRB-approved research protocol, any applicable investigator brochure, and the current IRB-approved informed consent document and other relevant sources of information, such as product labeling and package inserts.)

**AND**

CONFIDENTIAL

Related to the research procedures (An event is “related to the research procedures” if in the opinion of the principal investigator or sponsor, the event was more likely than not to be caused by the research procedures.)

### **Reporting Process**

Unanticipated problems posing risks to subjects or others as noted above will be reported to the IRB as a written or online report of the event (including a description of the event with information regarding its fulfillment of the above criteria, follow-up/resolution and need for revision to consent form and/or other study documentation).

Copies of each report and documentation of IRB notification and receipt will be kept in the Clinical Investigator’s study file.

### **Reporting Deaths: more rapid reporting requirements**

Concerning deaths that occur during the course of a research study, the following describes the more rapid reporting requirement of the IRB for specific situations:

1. Report the event within 24 hours when the death is unforeseen (unexpected) and indicates participants or others are at increased risk of harm.
2. Report the event within 72 hours, for all other deaths, regardless of whether the death is related to study participation.

For reportable deaths, the initial submission to the IRB may be made through the eIRB system. The AE/Unanticipated Problem Form is required as a follow up to the initial submission.

### **Other Reportable events:**

For clinical drug trials, the following events are also reportable to the IRB:

1. Any adverse experience that, even without detailed analysis, represents a serious unexpected adverse event that is rare in the absence of drug exposure (such as agranulocytosis, hepatic necrosis, Stevens-Johnson syndrome).
2. Any adverse event that would cause the sponsor to modify the investigators brochure, protocol or informed consent form, or would prompt other action by the IRB to assure protection of human subjects.
3. Information that indicates a change to the risks or potential benefits of the research, in terms of severity or frequency. For example:
  - An interim analysis indicates that participants have a lower rate of response to treatment than initially expected.
  - Safety monitoring indicates that a particular side effect is more severe, or more frequent than initially expected.
  - A paper is published from another study that shows that an arm of your research study is of no therapeutic value.
4. Change in FDA safety labeling or withdrawal from marketing of a drug, device, or biologic used in a research protocol.
5. Breach of confidentiality

CONFIDENTIAL

6. Change to the protocol taken without prior IRB review to eliminate apparent immediate hazard to a research participant.
7. Incarceration of a participant when the research was not previously approved under Subpart C and the investigator believes it is in the best interest of the subject to remain on the study.
8. Complaint of a participant when the complaint indicates unexpected risks or the complaint cannot be resolved by the research team.
9. Protocol violation (meaning an accidental or unintentional deviation from the IRB approved protocol) that in the opinion of the investigator placed one or more participants at increased risk, or affects the rights or welfare of subjects.

### **8.3.3 Reporting obligations to the ACC DSMC**

The Abramson Cancer Center has developed a detailed data safety and monitoring plan. The Clinical Trials Scientific Review and Monitoring Committee (CTSRMC) serves as a rigorous scientific peer review mechanism for all cancer protocols conducted within the University of Pennsylvania. The CTSRMC's focus is the scientific merit, priorities, and progress of Cancer Center clinical research while the DSMC's focus is data quality and subject safety monitoring and auditing. The guidelines governing both committees have been adapted from the NCI/NIH policies.

The DSMC requires AE/SAE submission through Velos as follows

- All grade 3 or higher events, including GVHD, within 5 business days of knowledge of the adverse event. Grade 3 and 4 events that are typical in the disease population, with the exception of those that could be symptoms/early indicators of any of the toxicities defined in the Toxicity Management section of the protocol, signs/symptoms of an allergic response, severe hypotensive crisis or any other reaction to the infusion, do not require DSMC reporting. It is important to note that these events must be reported in the absence of a diagnosis of a specific toxicity.
- All unexpected deaths within 24 hours of knowledge
- All other deaths within 30 days of knowledge (including death of subjects off study)
- In the event of a grade 4 or 5 unexpected event regardless of attribution, the investigators and the study team must meet or have a teleconference within 24 business hours of the event to have a thorough discussion of the event. These types of events will not be vetted via e-mail. The sponsor should not be involved in discussions about attribution.

### **8.3.4 FDA Notification by Sponsor**

The study sponsor is required to report certain study events in an expedited fashion to the FDA. These written notifications of adverse events are referred to as IND safety reports. The sponsor must report an IND safety reports as described in:

<http://www.fda.gov/downloads/Drugs/GuidanceComplianceRegulatoryInformation/Guidances/UCM227351.pdf>.

CONFIDENTIAL

### ***Within 7 calendar days***

#### Any study event that is:

- *Unexpected* fatal or life-threatening *suspected adverse reaction*.
- Expected and unexpected Grade 3 or higher events of cytokine release syndrome per the modified CRS grading scale in Table 8-1
- All fatal events occurring within 30 days of T-cell infusion, regardless of attribution and expectedness

### ***Within 15 calendar days***

#### Any study event that is:

- Serious and unexpected
  - Suspected adverse reaction serious, but not fatal or life-threatening
- or-
- a previous adverse event that was not initially deemed reportable but is later found to fit the criteria for reporting (reporting within 15 calendar days from when event was deemed reportable).

#### Any finding from other studies, findings from animal or in vitro testing:

- that suggest a significant risk for human subjects including reports of mutagenicity, teratogenicity, carcinogenicity or reports of significant organ toxicity at or near the expected human exposure.

#### Increase in rate of occurrence of serious suspected adverse reactions:

- any clinically important increase in the rate of a serious suspected adverse reaction over that listed in the protocol or investigator brochure

### **Additional reporting requirements**

Sponsors are also required to identify in IND safety reports all previous reports concerning similar adverse events and to analyze the significance of the current event in light of the previous reports.

If the adverse event does not meet expedited reporting requirements, the Sponsor will report the SAE as in the IND Annual Report.

### **Reporting Process**

Adverse events may be submitted on FDA Form 3500A or in a narrative format.

#### **8.4 Toxicity Management, Stopping Rules and Study Termination**

It is expected that AEs will occur frequently in this population based on the underlying advanced hematologic malignancy and these can be SAEs. Therefore, there is no specific occurrence of SAEs that define a stopping rule, but the review of SAEs will form the basis for potential early stopping of the study. Only unexpected SAEs that are related to the CART-19 cells would define a stopping rule. The review of these adverse events, and any decision to prematurely stop subject enrollment, will be determined by the DSMB and reviewed by the IRB.

CONFIDENTIAL

Premature termination of the clinical trial may occur because of a regulatory authority decision, change in opinion of the IRB, the DSMB, or determination that there are problems in the cell product generation or safety at the discretion of the study investigators. Additionally, recruitment may be stopped for reasons of particularly low recruitment, protocol violations, or inadequate data recording.

#### **8.4.1 Criteria for stopping or pausing the study**

The study will be stopped if:

- Any subject develops uncontrolled T cell proliferation that does not respond to management.
- The Investigator, Study Funder, Sponsor, DSMB, ACC DSMC, or any independent review board or regulatory body decides for any reason that subject safety may be compromised by continuing the study.
- The Sponsor or Study Funder decides to discontinue the development of the intervention to be used in this study.

The protocol will be paused pending submission of protocol pause to the FDA and review by the IRB and DSMB if any patient experiences any of the following events within two weeks of the CART-19 infusion:

- Life-threatening (grade 4) toxicity attributable to protocol therapy that is unmanageable, unexpected, unrelated to chemotherapy, and attributable to protocol therapy. This includes grade 4 GVHD. In terms of expected toxicity, we expect high fevers, hypotension, possible ICU admission and even mechanical ventilation. CRS and MAS can result in grade 4 liver toxicity, nephrotoxicity and other organ involvement. In addition, we have seen reversible confusion in 3 patients which fully resolved spontaneously over 2-4 days without treatment or sequelae.
- Death.
- If the V $\beta$  analysis pattern of insertion is found to favor a single dominant insertion site pattern the clinical trial will be placed on hold for dosing to allow evaluation of the subject in consultation with gene therapy experts, study investigators, DSMB, FDA and NIH.

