## **4 SUBJECT SELECTION AND WITHDRAWAL**

### **4.1 Inclusion Criteria**

Inclusion criteria are designed to include a broad spectrum of subjects with documented CD19+ hematologic malignancies. Enrollment at CHOP will largely be limited to ALL and high-grade B cell NHL. Male and female subjects with CD19+ B cell malignancies in patients with no available curative treatment options (such as autologous or allogeneic SCT) who have limited

CONFIDENTIAL

prognosis (several months to <2 year survival) with currently available therapies will be enrolled:

1. Eligible diseases: CD19+ leukemia or lymphoma
  - a. ALL without curative options for therapy, including those not eligible for allogeneic SCT because of:
    - age
    - comorbid disease
    - other contraindications to TBI-based conditioning (required for ALL SCT)
    - lack of suitable donor
    - prior SCT
    - Declines allo SCT (in CR3) as a therapeutic option after documented discussion about the role of SCT with a BMT physician not part of the study team (see note below).
  - Patient may be in any complete response, or patient may have active disease but responding or stable after most recent therapy (see 5.2 Patient Eligibility to Receive CART-19 Transduced T Cells, below). The intent is not to enroll patients with no degree of disease control, or rapidly increasing disease burden between enrollment and cell infusion.
  - b. Follicular lymphoma, previously identified as CD19+
    - At least 2 prior combination chemotherapy regimens (not including single agent monoclonal antibody (Rituxan) therapy).
    - Stage III-IV disease.
    - Less than 1 year between last chemotherapy and progression (i.e. most recent progression free interval <1 year).
    - Disease responding or stable after most recent therapy (chemotherapy, MoAb).
  - c. CLL
    - At least 2 prior chemotherapy regimens (not including single agent monoclonal antibody (Rituxan) therapy).
    - Less than 1 year between last chemotherapy and progression (i.e. most recent progression free interval <1 year).
    - Not eligible or appropriate for conventional allogeneic SCT.
    - Disease responding or stable after most recent therapy (chemotherapy, MoAb)
  - d. Mantle cell lymphoma
    - Beyond 1st CR with relapsed or persistent disease and not eligible or appropriate for conventional allogeneic or autologous SCT.
    - Disease responding or stable after most recent therapy (chemotherapy, MoAb).

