## **5 STUDY DRUG**

### **5.1 Description**

CART-19 cells are autologous T cells (collected from the patient) that have been engineered to express an extracellular single chain antibody (scFv) with specificity for CD19 linked to an intracellular signaling molecule comprised of a tandem signaling domain of the 4-1BB and TCR $\zeta$  signaling modules. The CART-19 cells are cryopreserved in infusible cryomedia and will be administered in either 1 or 2 bags. Each bag will contain an aliquot (volume dependent upon dose) of cryomedia containing the following infusible grade reagents: plasmalyte-A, dextrose, NaCl, up to 7.5% DMSO, dextran 40, human serum albumin with up to  $5 \times 10^9$  autologous T cells per bag.

Expected toxicities associated with infusion of CART-19 cells include transient fever, chills, nausea, and rigors. In order to minimize these events, patients will receive premedication as instructed below in section 5.4. Later toxicities (7-21 days post infusion) are likely to be related to cytokine release syndrome (CRS), or possibly tumor lysis. Toxicities that could potentially occur but are unprecedented are primarily related to the gene transfer and are described in Section 8.4.2. These include generation of a replication competent lentivirus (RCL), insertional oncogenesis, and uncontrolled proliferation of the CART-19 cells.

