### **6.6 CART-19 Infusion #1 With Intra-Patient Dose Escalation**

Infusions may begin a minimum of 1 to 5 days after completion of chemotherapy.

The day of (but prior to) the first infusion, patients will have a CBC with differential, and assessment of CD3, CD4 and CD8 counts since chemotherapy is given in part to induce lymphopenia.

All patients must undergo a rapid influenza diagnostic test during the flu season months of October through May and within 10 days prior to the planned CART-19 infusion. If the patient is positive for influenza, oseltamivir phosphate or zanamivir should administered for 10 days as preventative treatment. The patient must complete their 10 day preventative treatment course prior to receiving CART-19. The test does not need to be repeated prior to CART-19 infusion however if flu-like or respiratory signs and symptoms are present, CART-19 infusion should be delayed until the patient is asymptomatic.

CART-19 transduced T cells will be given, up to a total dose of  $1.5 \times 10^7$ - $5 \times 10^9$  ( $0.3 \times 10^6$ - $1.0 \times 10^8$ /kg) total cells transduced with the 41BB-z vector. We will use the following schedule, starting with a 10x dose reduction but allowing for intra-patient dose escalation:

- Day 0: 10% of total dose
- Day 1: 30% of total dose if patient is stable from prior dose (no significant toxicity such as fever from 10% dose). This dose may be given between day 1 and 4 if the patient develops transient fever and is subsequently afebrile and clinically stable. If not given on day 1-4, this dose will then become available for infusion at day 14 or later (see next paragraph regarding timing and subsequent infusions).

**Timing and doses of subsequent CART-19 infusions.** For patients who have had i) evidence of brief B cell aplasia with subsequent B cell recovery (suggesting rapid CAR clearance), or ii) fever and other reversible toxicities without evidence of CAR expansion/LGLs or response, or iii) no response, or a partial or temporary response to the initial infusion, it may be that the initial dose of cells was not adequate to produce a full therapeutic effect, or the cells may not have persisted long enough to produce longer-term disease control. In these cases, it may be

CONFIDENTIAL

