Regardless of timing, toxicities that would preclude a subsequent dose of T cells are DLTs (defined in section 8.1) or GVHD attributable to the cell infusion, and not non-DLT toxicities or toxicities attributable to the prior chemotherapy, such as cytopenias. A DLT will prevent the infusion of the next dose, even if fully resolved by that time.

The cells are thawed by the [REDACTED]. The thawed cells will be given as a slow IV push or infusion rate as quickly as tolerated so that the duration of the infusion will be approximately 10-15 minutes, adjusted for size of patient and volume of infusion. In subjects 15-20 who receive mixtures of CART-19 cells, in order to facilitate mixing, the cells may be administered simultaneously using a Y-adaptor. Subjects will be infused and premedicated as described in section 5.3. Subjects' vital signs will be assessed and pulse oximetry will be done prior to dosing, at the end of the infusion and every 15 minutes thereafter for 1 hour and until these are stable and satisfactory. A blood sample for determination of baseline CART-19 level is obtained before infusion.

Patients experiencing toxicities from their preceding cytoreductive chemotherapy will have their infusion schedule delayed until these toxicities have resolved. The specific toxicities warranting delay of T cell infusions include: 1) Pulmonary: Requirement for supplemental oxygen to keep

CONFIDENTIAL

saturation greater than 95% or presence of radiographic abnormalities on chest x-ray that are progressive; 2) Cardiac: New cardiac arrhythmia not controlled with medical management. 3) Hypotension requiring pressor support. 4) Active Infection: Positive blood cultures for bacteria, fungus, or virus within 48 hours of T cell infusion. These delay criteria apply to subsequent doses of CART-19 cells as well.

A serum sample for potassium and uric acid will be collected before each infusion.

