### **Dose Limiting Toxicity (DLT)**

Dose limiting toxicity is defined as a grade 3 or 4 toxicity as determined by CTC 3.0, which is unmanageable, unexpected and unrelated to chemotherapy and attributable to protocol therapy. For instance, grade 4 neutropenia or thrombocytopenia related to pre-infusion chemotherapy would not be related to study drug and would not be considered as a

CONFIDENTIAL

DLT. In addition, if the toxicity is autoimmune or allergic in nature and occurs after repeat dosing, a grade 2 toxicity will be considered a DLT.

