#### **CTL019-Therapy-Associated Grading for Cytokine Release Syndrome: The Penn Grading Scale for Cytokine Release Syndrome (PGS-CRS)**

- Marked elevations in IL-6, interferon gamma and less intensely TNF
- Symptoms occur 1 to 14 days after cell infusion in ALL
- Symptoms may include: High fevers, rigors, myalgia, arthralgia, nausea, vomiting, anorexia, fatigue, headache, hypotension, encephalopathy, dyspnea, tachypnea, and hypoxia
- The start date of CRS is a retrospective assessment of the date of onset of persistent fevers and/or myalgia consistent with CRS and not explained by other events (i.e. sepsis). The stop date of CRS is defined as the date when the patient has been afebrile for 24 hours and off vasopressors for 24 hours.

CONFIDENTIAL

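### The general automatic pause in section 8.4.1 ends two weeks after an unspecified CART-19 infusion, short of the 7-21 day period that section 5.1 gives for later product toxicity

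*Combined protocol and SAP*

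**What the plan says.** Section 8.4.1 pauses the protocol until the pause has been submitted to the FDA and the IRB and DSMB have reviewed it. The trigger applies "if any patient experiences any of the following events within two weeks of the CART-19 infusion". The listed events include death from any cause and grade 4 toxicity that is unexpected, unmanageable, unrelated to chemotherapy and attributable to protocol therapy. Grade 4 GVHD is named as included. Expected CRS-type toxicity is described separately and does not meet the grade 4 condition.

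Two places describe the timing of product toxicity:

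- Section 5.1: "Later toxicities (7-21 days post infusion) are likely to be related to cytokine release syndrome (CRS), or possibly tumor lysis".
- The CRS grading scale in section 8.4.4: "Symptoms occur 1 to 14 days after cell infusion in ALL". ALL is a main disease here, since "Enrollment at CHOP will largely be limited to ALL and high-grade B cell NHL" (section 4.1).

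Dosing is split. The Study Summary gives 10% on day 0, 30% on day 1 and possibly 60% on day 14 or later. Section 6.6 lets the second dose slip to day 4 and adds: "If not given on day 1-4, this dose will then become available for infusion at day 14 or later".

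Section 8.4 has a general statement with no time limit, "Only unexpected SAEs that are related to the CART-19 cells would define a stopping rule", but leaves any decision to stop enrollment to the DSMB, with IRB review.

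**The concern.** An automatic pause ensures that other patients are not dosed while a serious event is being understood. The sponsor judged that deaths and unexpected attributable grade 4 events warrant this without waiting for anyone's discretion. The protection then ends at two weeks, and the text available for review gives no reason for that length.

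Two things are at stake. First, a CART-19-related death on, say, day 18 falls inside the period that section 5.1 names, yet requires no pause. Second, because the anchor infusion is undefined, a patient given a dose on day 14 or later may have two weeks of cover after that dose or essentially none, depending on how 8.4.1 is read. Section 7.1 also makes failure to complete because of the stopping rules the main basis for judging safety and feasibility, so the reach of these rules matters to the trial's conclusion as well as to patients.

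**Working it through.** The plan states no operating characteristics for the pause, so there is no figure to reproduce. The check compares time windows and then asks what else would apply after the window.

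**1. Window against the stated toxicity period.** Section 5.1 covers days 7 to 21: 21 - 7 + 1 = 15 days. A 14-day window covers days 7 to 14: 14 - 7 + 1 = 8 days. Outside it are 15 - 8 = 7 days (days 15-21). Against the CRS scale's days 1-14 in ALL, no days fall outside. The CNS3 cohort is staggered by 21 days for toxicity monitoring (section 4.3), which agrees with 5.1.

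**2. Effect of the undefined clock, for a dose on day 14.** The 7-21 day period after that dose is study days 14 + 7 = 21 to 14 + 21 = 35.

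- Clock from day 0: cover ends on day 14, so all 15 days lie outside.
- Clock restarting at each dose: cover runs to 14 + 14 = 28, so days 21-28 (8 days) are inside and days 29-35 (7 days) outside.

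**3. Mandatory actions with no two-week limit.**

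- Uncontrolled T cell proliferation that does not respond to management: study stop (8.4.1).
- Attributable grade 5 neurological toxicity, or grade 3/4 neurological or psychiatric toxicity unresolved at 4 weeks: stop to CNS3 accrual only (8.4.2).
- Second positive RCL test: infusions halted (8.4.3).
- Dominant insertion site: dosing hold, stated in 8.4.3 without a window.

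Each depends on a specific cause. None covers a related death or an unexpected attributable grade 4 event from another cause, such as GVHD.

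**4. What such an event does trigger after the window.**

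- Sponsor: SAE report within 24 hours (8.3.1).
- ACC DSMC: unexpected deaths within 24 hours, and most grade 3 or higher events, including GVHD, within 5 business days (8.3.3).
- Study team: meeting within 24 business hours for unexpected grade 4-5 events (8.3.3).
- IRB: deaths within 24 or 72 hours; unexpected related events within 10 working days (8.3.2).
- FDA: 7 days for all deaths within 30 days of infusion and for unexpected life-threatening suspected reactions (8.3.4).
- DSMB review (8.4), and the power of the investigator, funder, sponsor, DSMB, DSMC or a regulator to stop the study (8.4.1).

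These routes are fast, and several reach bodies that can stop the study. None of them by itself requires dosing of other patients to halt.

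**5. Why not simply extend the all-cause death trigger.** Assume exponential survival from infusion with median m days and L = ln 2 / m. Expected all-cause deaths on days 15-21 among 72 infused patients are 72 × (exp(-14L) - exp(-21L)).

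- m = 84 (12 weeks, the minimum expected survival in 4.1): 3.60
- m = 183: 1.79
- m = 365: 0.93
- m = 730 (the two-year upper end of prognosis in 4.1): 0.47

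That would add roughly 0.5 to 3.6 deaths to the trigger whether or not CART-19 caused them. An attribution test for the added period is meant to limit pauses for disease deaths.

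**The case against.** The best defense is that two weeks fits the main hazard. The CRS scale puts symptoms at days 1-14 in ALL. Section 5.1's longer period concerns CRS and possible tumor lysis, and 8.4.1 treats CRS-type toxicity as expected, so it would not meet the unexpected grade 4 condition anyway. This stands in part. It means the 7-21 day period supports an extension mainly for deaths, where 8.4.1 sets no expectedness condition. It does not settle the matter, because the timing of symptom onset does not bound when a death follows, and CHOP also enrolls high-grade NHL.

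For GVHD the documents give no timing, and the Introduction reports none in 10 post-allo patients. Twenty-one days is therefore not derived for GVHD.

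A reader might contrast the pause with the DLT definition in 8.1, which describes the toxicity as one "which is unmanageable, unexpected and unrelated to chemotherapy and attributable to protocol therapy" with no window, and with 6.6: "A DLT will prevent the infusion of the next dose, even if fully resolved by that time". That is a difference in scope and not a contradiction: barring one patient's next dose and pausing a trial serve different purposes.

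A reader might also infer that after day 14 nothing mandatory remains. The cause-specific rules in 8.4.1 to 8.4.3 show otherwise, and day 14 as the cut-off itself presumes a clock from day 0. Finally, part of 6.6 on subsequent infusions and the DSMB charter are not in the text available for review. Either could define the anchor or add triggers.

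**Conclusion.** The point holds in a limited form. The only general study-wide automatic pause for death and for unexpected, unmanageable, attributable grade 4 toxicity lasts two weeks from an undefined infusion. It leaves out 7 of the 15 days that section 5.1 gives for later toxicity. On a day-0 reading, it also leaves out the whole of that period after a dose on day 14 or later. Outside the cause-specific rules, a later related death or qualifying grade 4 event leads to expedited reporting and discretionary action.

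The documents give no late-event rate, so neither a probability of a missed event nor a number of patients harmed can be stated. It would be tempting to count the infusions that could occur before a reporting deadline, but that would not measure harm: several bodies able to stop the study would know within days, and a reporting deadline is not when exposure ends.

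This is a cheap improvement to a rule that falls short of the protocol's own risk period. Confidence is medium, because the missing part of 6.6 and the charter could narrow the gap.

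**What to change.** Amend section 8.4.1 as follows:

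- State that the pause clock restarts at each CART-19 infusion, including doses on day 14 or later.
- Keep the all-cause death trigger at two weeks.
- Extend the pause to at least 21 days after each infusion, matching section 5.1 and the CNS3 stagger, for (a) death attributable to CART-19 under the more-likely-than-not standard already in 8.3.2 and 8.4.2, and (b) unexpected, unmanageable grade 4 toxicity attributable to protocol therapy, including grade 4 GVHD.

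If only one change is made, define the anchor infusion. It is one sentence and affects every patient who receives a later dose.

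The cost is an amendment to protocol wording and possibly a few more pauses. Using the existing attribution standard, and not a looser possibly-related test, should limit pauses for late deaths from disease or from infection. Section 8.4.2 already treats infection as less likely to be due to CART-19. No sample size, endpoint or analysis changes.
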